### **7.2.2 SAE reporting**

To ensure patient safety, every SAE, regardless of suspected causality, occurring after the patient has provided informed consent and until 30 days after the patient has stopped study participation (defined as time of last dose of study drug taken or last visit whichever is later) must be reported to Novartis within 24 hours of learning of its occurrence.

Any SAEs experienced after this 30 days period should only be reported to Novartis if the investigator suspects a causal relationship to the study drug.

All follow-up information for the SAE including information on complications, progression of the initial SAE and recurrent episodes must be reported as follow-up to the original episode within 24 hours of the investigator receiving the follow-up information. An SAE occurring at a different time interval or otherwise considered completely unrelated to a previously reported one must be reported separately as a new event.

Paper SAE form will be used in this study. Information about all SAEs is collected and recorded on the Serious Adverse Event Report Form. The investigator must assess the relationship of any SAE to study drug, complete the SAE Report Form in Japanese and send the completed, signed form by fax within 24 hours to the local Novartis Drug Safety and Epidemiology Department (DS&E). The telephone and telecopy number of the contact persons in the local department of Clinical Safety and Epidemiology, specific to the site, are listed in the investigator folder provided to each site. The original copy of the SAE Report

Form and the fax confirmation sheet must be kept with the eCRF documentation at the study site.

Follow-up information is sent to the same person to whom the original SAE Report Form was sent, using a new SAE Report Form stating that this is a follow-up to the previously reported SAE and giving the date of the original report. The follow-up information should describe whether the event has resolved or continues, if and how it was treated, whether the blind was broken or not (where applicable), and whether the patient continued or withdrew from study participation.

If the SAE is not previously documented in the Investigator's Brochure or Package Insert (new occurrence) and is thought to be related to the study treatment a DS&E Department associate may urgently require further information from the investigator for health authority reporting. Novartis may need to issue an Investigator Notification (IN) to inform all investigators involved in any study with the same study treatment that this SAE has been reported. Suspected Unexpected Serious Adverse Reactions (SUSARs) will be collected and reported to the competent authorities and relevant ethics committees in accordance with EU Guidance 2011/C 172/01 or as per national regulatory requirements in participating countries.

### **7.3 Liver safety monitoring**

Not applicable.

### **7.4 Renal safety monitoring**

Not applicable.

### **7.5 Reporting of study treatment errors including misuse/abuse**

Medication errors are unintentional errors in the prescribing, dispensing, administration or monitoring of a medicine while under the control of a healthcare professional, patient or consumer.

Misuse refers to situations where the medicinal product is intentionally and inappropriately used not in accordance with the protocol.

Abuse corresponds to the persistent or sporadic, intentional excessive use of a medicinal product, which is accompanied by harmful physical or psychological effects.

Study treatment errors and uses outside of what is foreseen in the protocol will be collected in the DAR eCRF irrespective of whether or not associated with an AE/SAE and reported to Safety only if associated with an SAE. Misuse or abuse will be collected and reported in the safety database irrespective of it being associated with an AE/SAE. Guidance for capturing study treatment errors including misuse/abuse is given in [Table 7-1](#).

**Table 7-1 Guidance for capturing the study treatment errors including misuse/abuse**

Treatment error type	Document in Dose Administration (DAR) eCRF (Yes/No)	Document in AE eCRF	Complete SAE form
Unintentional study treatment error	Yes	Only if associated with an AE	Only if associated with an SAE
Misuse/Abuse	Yes	Yes,	Yes, even if not associated with a SAE

## **7.6 Pregnancy reporting**

To ensure patient safety, each pregnancy occurring after signing the informed consent must be reported to Novartis within 24 hours of learning of its occurrence. The pregnancy should be followed up to determine outcome, including spontaneous or voluntary termination, details of the birth, and the presence or absence of any birth defects, congenital abnormalities, or maternal and/or newborn complications. If any birth defects/congenital anomaly noted, it should be reported as SAE separately.

Pregnancy must be recorded on the Pharmacovigilance Pregnancy Form and reported by the investigator to the local Novartis DS&E Department. Pregnancy follow-up should be recorded on the same form and should include an assessment of the possible relationship to the Novartis study drug of any pregnancy outcome. Any SAE experienced during pregnancy must be reported on the SAE Report Form.

## **7.7 Prospective suicidality assessment**

Not applicable.

# **8 Data review and database management**

## **8.1 Site monitoring**

Before study initiation, at a site initiation visit or at an investigator's meeting, a Novartis representative will review the protocol and eCRFs with the investigators and their staff. During the study, the field monitor will visit the site regularly to check the completeness of patient records, the accuracy of entries on the eCRFs, the adherence to the protocol and to Good Clinical Practice, the progress of enrollment, and to ensure that study drug is being stored, dispensed, and accounted for according to specifications. Key study personnel must be available to assist the field monitor during these visits.

The investigator must maintain source documents for each patient in the study, consisting of case and visit notes (hospital or clinic medical records) containing demographic and medical information, laboratory data, and the results of any other tests or assessments. All information on eCRFs must be traceable to these source documents in the patient's file. The investigator

must also keep the original informed consent form signed by the patient (a signed copy is given to the patient).

The investigator must give the monitor access to all relevant source documents to confirm their consistency with the eCRF entries. Novartis monitoring standards require full verification for the presence of informed consent, adherence to the inclusion/exclusion criteria, documentation of SAEs, and the recording of data that will be used for all primary and safety variables. Additional checks of the consistency of the source data with the eCRFs are performed according to the study-specific monitoring plan. No information in source documents about the identity of the patients will be disclosed.

## **8.2 Data collection**

Field monitors will review the eCRFs for completeness and accuracy and instruct site personnel to make any required corrections or additions. The designated investigator staff will enter the data required by the protocol into the eCRF. The eCRFs have been built using fully validated secure web-enabled software that conforms to 21 CFR Part 11 requirements. Investigator site staff will not be given access to the EDC system until they have been trained. Automatic validation programs check for data discrepancies in the eCRFs and, allow modification or verification of the entered data by the investigator staff.

The Principal Investigator is responsible for assuring that the data entered into eCRF is complete, accurate, and that entry and updates are performed in a timely manner.

## **8.3 Database management and quality control**

Novartis personnel (or designated Contract Research Organization; CRO) will review the data entered by investigational staff for completeness and accuracy. Electronic data queries stating the nature of the problem and requesting clarification will be created for discrepancies and missing values and sent to the investigational site via the EDC system. Designated investigator site staffs are required to respond promptly to queries and to make any necessary changes to the data.

Concomitant treatments and prior medications entered into the database will be coded using the World Health Organization (WHO) Drug Reference List, which employs the Anatomical Therapeutic Chemical classification system. Medical history/current medical conditions and AEs will be coded using the Medical dictionary for regulatory activities (MedDRA) terminology.

Laboratory samples will be processed centrally and the results will be sent electronically to the Novartis/designated CRO. The Novartis/CRO data management staff will perform a reconciliation of the data entered into the eCRF versus what is received from the central laboratory. At a minimum, this reconciliation will include header reconciliation, visit window checks, duplicate record checks, out of range checks as defined by the Clinical Trial Team and checks to address missing laboratory data.

Randomization codes and data about all study treatments dispensed to the patient will be tracked in the drug dispensing log eCRF. The occurrence of any protocol violations will be determined. After these actions have been completed and the data has been verified to be

complete and accurate, the database will be declared locked and made available for data analysis.

Authorization is required prior to making any database changes to locked data, by the Medical Advisor or Equivalent; prior authorizing the database un-lock, a CTT meeting will be hosted, to discuss the issues leading to database unlock and update. For EDC studies, after database lock, the investigator will receive paper copies of the patient data for archiving at the investigational site.

#### **8.4 Data Monitoring Committee**

Not required.

#### **8.5 Adjudication Committee**

Not required.

### **9 Data analysis**

The statistical analysis will be performed by Product Lifecycle Services (PLS) of Novartis.

The primary objective is to demonstrate that PRN regimen of 0.5 mg ranibizumab with Grid&Direct short pulse laser photocoagulation reduces the burden of frequent ranibizumab injections as compared to ranibizumab monotherapy.

The primary objective will be assessed by the mean number of ranibizumab injections applied up to Month 11.

Summary statistics for continuous variables will generally include the number of patients (N), minimum, lower quartile, mean, median, upper quartile, and maximum. For categorical or binary variables, the number and percent of patients in each category will be presented. P-values presented will be 2-sided unless otherwise specified.

Data analyses will be presented at all time points assessed, by treatment group including graphical presentations, where appropriate. For statistical analysis purpose, baseline values will be considered to be the last available values collected before Day 1. Day 1 will be defined for statistical analysis purpose as the time point of first treatment (associated to baseline visit).

For patients who receive a prohibited medication for the study indication in the study eye, the efficacy data will be excluded from the per-protocol efficacy analysis.

Further details will be provided in the statistical analysis plan (SAP).

#### **9.1 Analysis sets**

The **Randomized Set** will consist of all randomized patients.

**The Full Analysis Set (FAS)** will consist of all randomized patients who received at least one administration of ranibizumab injection. In case there are safety concerns after administration of laser photocoagulation at Baseline (Day 1) and ranibizumab injection is not given during the entire study, the patient will still be included in the FAS, as there was an intention to treat

the patient with ranibizumab. Following the intent-to-treat principle, patients will be evaluated according to the treatment assigned to at randomization.

No data will be excluded from the FAS analyses because of protocol deviations.

**The Per Protocol Set (PPS)** will consist of all patients in the FAS who received at-least the first mandatory administration of ranibizumab injection and have at least one post-baseline assessment for BCVA and have no clinically significant protocol deviations.

Clinically significant protocol deviations will be defined in the Statistical Analysis Plan. The criteria and determination of clinically relevant protocol deviations and patient specific identification of data to be excluded from the PPS will be databased and finalized prior to database lock.

The **Safety Set** will consist of all patients who received at least one administration of ranibizumab injection and had at least one post-baseline safety assessment. The statement that a patient had no AEs also constitutes a safety assessment. Patients will be evaluated according to treatment received.

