### **9.4.2 Statistical model, hypothesis, and method of analysis**

The primary analysis will be conducted at Month 12 within the FAS using observed data.

The following 1-sided hypothesis will be tested at the alpha level of 0.025:

$H_0: \mu_{\text{Ranibizumab-Laser}} - \mu_{\text{Ranibizumab-Mono}} = 0$  versus

$H_1: \mu_{\text{Ranibizumab-Laser}} - \mu_{\text{Ranibizumab-Mono}} \leq 0$

where  $\mu_{\text{Ranibizumab-Laser}}$  and  $\mu_{\text{Ranibizumab-Mono}}$  are the unknown mean values of the number of ranibizumab injections for the related treatment arms up to Month 11.

The statistical hypothesis testing of the number of ranibizumab treatments will be based on a stratified Cochran-Mantel-Haenszel (CMH) test. Stratification will be done based on categories of baseline decimal VA ( $<0.3$ , or  $\geq 0.3$ ). Difference of mean number of injections, 95% confidence interval (CI) of difference and one-sided p-value of the CMH test will be reported.

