### **9.4.3 Handling of missing values/censoring/discontinuations**

No imputation is required for the primary endpoint which is number of ranibizumab injections, based on PRN regimen that is the number of injections during the study period will be used for the primary endpoint.

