## **9.8 Sample size calculation**

In order to detect a clinically meaningful difference in the number of injections (at least 2 injections) at Month 11, as suggested by the principal investigators, this study will randomize at least 56 patients (28 per arm).

For the sample size calculation, we will assume a difference between arms of 2 injections and a standard deviation (SD) of 2.32 (based on CAVNAV study (Liegler et al. 2014)). Based on the non-parametric Wilcoxon-Mann Whitney test for the difference in means this would require 25 patients per arm with 80% power and a 0.025 significance level (1sided), however assuming approximate 10% drops out rate, a total of at least 56 patients (28 per arm) are required to be randomized.

Approximately 70 patients will need to be screened in order to have at least 56 patients eligible and commencing treatment in the trial.

All sample size calculations performed using EAST 6.0.

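### The FAS keeps an Arm 2 patient never injected after a Day 1 laser safety concern, and the primary analysis then scores that laser complication as the best possible result for laser

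*Protocol*

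**What the plan says.** Protocol 9.1 defines the FAS as "all randomized patients who received at least one administration of ranibizumab injection". It then makes one exception. If there are safety concerns after laser at Baseline (Day 1) and "ranibizumab injection is not given during the entire study, the patient will still be included in the FAS". The reason given is that ranibizumab treatment had been intended. No matching sentence covers a randomised patient who is not injected for a safety reason without having had laser.

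Section 9.4.2 sets the analysis: "The primary analysis will be conducted at Month 12 within the FAS using observed data". Section 9.4.3 says that no imputation is needed and that "the number of injections during the study period will be used for the primary endpoint". Section 9.4.4 repeats the analysis on the PPS, which by 9.1 requires the first mandatory injection. The Safety Set in 9.1 also requires an injection and has no laser exception.

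Two design facts complete the picture. Under 3.1 and 5.2, Arm 1 is ranibizumab monotherapy. Under 5.5.4, laser given on the same day must precede the injection by at least 30 minutes.

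**The concern.** Fewer injections is the favourable direction of the primary endpoint. The exception depends on an event that only the combination arm can have, and it adds only one possible value, 0. A laser complication that stops all ranibizumab would therefore enter the primary comparison as maximal laser benefit.

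The stated reason does not separate the arms. An Arm 1 patient who is randomised on Day 1 and then not injected for a safety reason was equally intended to receive ranibizumab, yet is dropped. With about 28 patients per arm, a single extreme value is visible in the mean and in the test.

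**Working it through.** **Step 1. Can the case occur, and in which arm?** Study laser is given only in Arm 2 (3.1, 5.2). Same-day laser comes before the injection (5.5.4), so a complication can prevent the first injection. Short of a protocol deviation, Arm 1 cannot meet the condition.

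**Step 2. What score does the patient get?** The analysis uses the FAS, observed data, the actual count and no imputation (9.4.2, 9.4.3), so the score is 0. Every other FAS patient entered by having at least one injection and scores 1 or more. The zero is not written out in the protocol, but it follows directly from these sections.

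**Step 3. The planned sample size.** Section 9.8 states: "we will assume a difference between arms of 2 injections and a standard deviation (SD) of 2.32". Noether's formula for the Wilcoxon-Mann-Whitney test, with one-sided alpha 0.025 and power 80%:
- p = Φ(2 / (2.32 × √2)) = 0.729
- n per arm = (1.960 + 0.842)² / (6 × (0.729 − 0.5)²) = 24.96, so 25
- 25 / 0.9 = 27.8, so 28 per arm and 56 in total

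This reproduces the plan, so 28 per arm and SD 2.32 are used below.

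**Step 4. Shift in the Arm 2 mean.** The protocol gives no expected mean count m, so m is an assumption. Replacing a typical count m by 0 in k of 28 patients lowers the mean by k × m / 28.

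| Assumed m | k = 1 | Share of the 2-injection target | k = 2 |
|---|---|---|---|
| 4 | 4/28 = 0.14 | 7% | 0.29 |
| 5 | 5/28 = 0.18 | 9% | 0.36 |
| 6 | 6/28 = 0.21 | 11% | 0.43 |
| 8 | 8/28 = 0.29 | 14% | 0.57 |

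**Step 5. One-sided error if the event has occurred.** Section 9.4.2: "The following 1-sided hypothesis will be tested at the alpha level of 0.025". The null simulation used 200,000 trials, 28 per arm, equal means, and rounded normal counts limited to 1–12 with SD 2.32. The test was an unstratified CMH mean-score test, rejecting at z < −1.96. The mean-score form is an assumption, because 9.4.2 does not name the form.

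| Assumed m | k = 0 | k = 1 | k = 2 | k = 3 |
|---|---|---|---|---|
| 4 | 2.5% | 3.8% | 5.9% | 8.9% |
| 5 | 2.5% | 4.0% | 6.5% | 10.2% |
| 6 | 2.5% | 4.3% | 7.1% | 11.4% |
| 8 | 2.4% | 4.6% | 8.1% | 14.0% |

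A stratified version at m = 5 gives about 2.4%, 4% and 6.5% for k = 0, 1 and 2. When the affected patients are left out instead of scored 0, the error is 2.4% to 2.6%, so the zero score drives the excess.

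**Step 6. Averaging over how often it happens.** The protocol gives no event rate. Take an assumed risk of 1% per Arm 2 patient and n = 28. The binomial probabilities of 0, 1, 2 and 3 cases are 0.755, 0.213, 0.029 and 0.003. A stratified run of 20,000 trials at m = 5 gave errors of 2.3%, 4.0%, 6.4% and 10.2%. The weighted error is 0.755 × 2.3 + 0.213 × 4.0 + 0.029 × 6.4 + 0.003 × 10.2 = 2.8%, against 2.3% with no case. At an assumed risk of 0.1% it is about 2.35%.

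**The case against.** Much of the case on the other side stands.

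- **Scope.** A reader might infer that the FAS keeps any never-injected Arm 2 patient. It does not. An Arm 2 patient with neither laser nor injection is dropped exactly as in Arm 1.
- **Keeping the patient is defensible.** The glossary and 5.5.4 count laser as study treatment, so this patient has received part of the assigned treatment and the excluded Arm 1 patient has received none. Deleting the exception would remove a patient after randomisation because of a complication of assigned treatment, which is worse.
- **Rarity.** Laser may be staged, deferred or postponed (5.5.4, 5.5.4.1), and the withholding reasons in 5.5.5 allow treatment to resume later. Never being injected afterwards needs an unusual course.
- **Sample size.** 28 per arm is a minimum. Amendment 2 reports 59 patients randomised with enrolment continuing, so each shift is slightly smaller.
- **Existing check.** The PPS repeat removes the patient, and 9.4.4 promises to look into major discrepancies. But the PPS also drops patients with clinically significant deviations or no post-baseline BCVA, so a difference between PPS and FAS could not be traced to this cause.
- **Estimand.** If assignment to laser truly leads to no injections, equal means by assigned arm is not strictly true. The error rates in the working refer to a laser that does not change the need for injections.

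None of this removes the central problem: a complication is scored as the best outcome, and no planned analysis isolates it.

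**Conclusion.** The point holds in a limited form. The direction of the bias follows from 9.1, 9.4.2 and 9.4.3 and needs no assumption. The size does. Each case lowers the Arm 2 mean by 0.14 to 0.21 injections for an assumed mean of 4 to 6. With an assumed mean of 5, one or two cases bring the one-sided error to about 4% or 6.5%.

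A reader might take these percentages as the error rate of the trial. They are not: they are conditional on one or two events having occurred. Averaged over an assumed 1% risk per patient, the rate is about 2.8%.

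A reader might also infer that analysing all randomised patients would cure the problem. It would make membership symmetric, but the laser complication would still score 0 and Arm 1 would still have no counterpart to it. The harm comes from how the patient is scored. The uneven membership rule and its reason are a secondary inconsistency.

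**What to change.** 1. In 9.1, keep the patient in the FAS and replace the laser-specific exception by one arm-neutral rule: either all randomised patients, or all randomised patients who received any study treatment (ranibizumab or laser). Under the second rule the never-injected Arm 1 patient stays outside, so the reason given must change from intention to treat to treatment received.
2. In 9.4.4, pre-specify a sensitivity analysis of the primary endpoint on the FAS. A FAS patient never injected for safety reasons, in either arm, is not credited with 0 but is given the Arm 1 mean count of the baseline VA stratum, or an unfavourable count.
3. Report the number of such patients by arm next to the primary result.

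The cost is a reworded sentence in 9.1, a short addition to 9.4.4 and one extra run. The supporting result may be slightly less favourable to laser. Under the all-randomised rule, untreated patients of either arm stay in the denominator. If no such patient occurs, the sensitivity analysis coincides with the primary one.

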Stop study participation	Point/time at which the patient came in for a final evaluation visit or when study/investigational treatment was discontinued whichever is later.
Study drug	Any drug administered to the patient or therapeutic procedure as part of the required study procedures; includes investigational drug and any control drugs or therapeutic procedure.

Study eye	The study eye is the eye selected by the investigator at Baseline (according to the protocol) to receive the study treatment.
Study treatment discontinuation	Point/time when patient permanently stops taking study treatment for any reason; may or may not also be the point/time of premature patient withdrawal.
Variable	Information used in the data analysis; derived directly or indirectly from data collected using specified assessments at specified time points.

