## 5.5.4 Instructions for prescribing and taking study treatment

For the entire trial, regardless of randomization, the following rules apply:

- Ranibizumab should be administered in the study eye on the day of the study visit. In any case, study treatment has to occur within the visit window as described in [Section 6](#).
- Treatments of the fellow eye with ranibizumab must not be performed on the same day as treatments with ranibizumab of the study eye.
- When ranibizumab and laser photocoagulation are to be applied on the same day to the same eye, the laser treatment has to be applied at least 30 minutes before the ranibizumab injection. When ranibizumab and laser photocoagulation are not to be applied on the same day to the same eye, laser treatment can be deferred for up to 14 days relative to the ranibizumab treatment.
- Initially, Grid&Direct short pulse laser photocoagulation may be performed in a staged manner as macular hemorrhage and severe edema (thicker than 400 µm as a guide) resolve, i.e. initial laser treatment can be split into 2 or more sessions.
- On days when ranibizumab and/or laser treatment is to be administered, efficacy assessments and pre-injection safety measures (tonometry, slit lamp and fundus examinations) must be conducted before administration of ranibizumab and/or laser photocoagulation.

If study visit assessments and a corresponding treatment occur on separate days, a repeat ophthalmoscopy should be performed as safety check-up before treatment of the eye. Results will be documented in the source documents but not in the eCRF. If any concern arises, treatment needs to be cancelled and a re-evaluation needs to take place. Efficacy assessments (BCVA, ██████) already performed at the scheduled study visit should not be repeated on the day of treatment unless the patient indicates a sudden change in vision.

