Instructions on how to prepare ranibizumab PFSs for intravitreal injection and its administration under aseptic conditions are provided in the package insert of the provided PFS. Information on pre- and post-injection procedures including administration of antibiotic eye drops is provided in [Appendix 2](#) and [Appendix 3](#), respectively. Laser photocoagulation should be applied as approved for the indication and further outlined below. Instructions on post-laser treatment procedures are outlined in [Appendix 4](#). Study treatment (ranibizumab, laser photocoagulation) prescribed and dispensed to the patient during the study must be recorded on the dosage administration record eCRF.

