### **5.6.2 Discontinuation of study treatment**

Patients can discontinue treatment because of the appearance of a new health condition suspected to require appropriate care or require medications prohibited by the protocol ([Section 5.5.8](#)), unacceptable AEs, refusal to continue treatment, or at the investigator's discretion based on his/her clinical judgment.

Study treatment *must* be discontinued under the following circumstances:

- Emergence of the following AEs:
  - Rhegmatogenous retinal detachment
  - Stage 3 or 4 macular hole
  - Stroke or transient ischemic attack (TIA)
- Pregnancy
- Use of prohibited treatment as per [Table 5-1](#).
- Any other protocol deviation that results in a significant risk to the patient's safety.

The reason for study treatment discontinuation will be recorded on the Treatment Period Completion eCRF.

Patients who permanently discontinue study treatment and start certain prohibited treatments (see [Table 5-1](#)) should be withdrawn from the study and undergo all assessments for the Visit 14 (End of study (EOS)) as described in [Table 6-1](#).

Patients who discontinue study treatment and do not start a prohibited medication per [Table 5-1](#) should NOT be considered withdrawn from the study and continue their scheduled follow-up assessments until Visit 14 (EOS). A Study Treatment Period Completion eCRF should be completed, giving the date and primary reason for stopping study treatment.

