- i. Tonometry: In the study eye, tonometry is conducted at every study visit in all treatment arms to assess IOP, regardless of treatment administration afterwards. On visits when ranibizumab and/or laser treatment is administered, also post-injection tonometry should be performed between 15 and 60 minutes after treatment in the study eye. In the fellow untreated eye, tonometry will be conducted at Screening, Baseline (Day 1), Month 6, and the EOS visit.

- k. These assessments are optional if the investigator requires the respective information to assess the need for retreatment.
- l. Before the study treatment with ranibizumab, ensure that patients have self-administered their antimicrobials 4 times daily for 3 days before each scheduled study treatment and instruct patients to self-administer their antimicrobials again 4 times daily for 3 days post-treatment with ranibizumab.
- m. In Arm 2, the first laser treatment must be given to the target within vascular arcades as soon as indicated, but can be deferred by a maximum of 14 days relative to the ranibizumab injection.
- n. Post injection safety after ranibizumab and/or laser treatment, comprising: central artery perfusion, vision check, IOP. (Perform finger count, hand motion, and light perception (when indicated) within 15 minutes post-treatment for the study eye only).
- o. Follow-up Contact: Contact the patient by telephone for safety evaluations 2 ( $\pm$  1) days following each study visit when study treatment (ranibizumab and/or laser photocoagulation) is administered.
- p. EOS: For patients, who complete, withdraw or are discontinued early (refer to [Section 5.6.2](#)) from the study, perform 30 days (+ 7 days) following the last study treatment or the last study visit.

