## **9.3 Treatments**

### **9.3.1 Study treatment**

Descriptive statistics will be provided to characterize study treatment using the Safety Set.

The number of patients receiving ranibizumab injections and laser treatments will be presented in frequency tables and cumulatively by treatment group. Summaries will be presented for the study eye only and for all ranibizumab injections/laser treatments in both the study eye and the fellow treated eye as appropriate. Other data related to the treatment or application procedure will be summarized as appropriate.

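### The Safety Set requires a ranibizumab injection, so the laser-only patient whom the FAS keeps drops out of the exposure and IOP summaries

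*Protocol*

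**What the plan says.** Protocol Section 9.1 defines the FAS as randomized patients with at least one ranibizumab injection, and then adds an exception. If there is a safety concern after Day 1 laser and "ranibizumab injection is not given during the entire study, the patient will still be included in the FAS". The Safety Set, defined in the same section, "will consist of all patients who received at least one administration of ranibizumab injection and had at least one post-baseline safety assessment". Its patients are analysed by treatment received, and it has no counterpart to the FAS exception.

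Elsewhere the protocol counts laser as study treatment. The glossary entry for study drug begins "Any drug administered to the patient or therapeutic procedure as part of the required study procedures". Section 5.5.4 states: "Study treatment (ranibizumab, laser photocoagulation) prescribed and dispensed to the patient during the study must be recorded". Section 9.5.2.1 accepts either an injection or laser as the first study treatment when it dates AE onset.

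Three places use the Safety Set in a way that matters here:
- Section 9.3.1: "Descriptive statistics will be provided to characterize study treatment using the Safety Set". These tables count patients receiving laser as well as injections.
- Section 9.3.3, for non-drug therapies and procedures.
- Section 9.5.2.4, for ocular assessments including IOP, both by visit and from before to after dosing.

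**The concern.** The authors saw the laser-only case and dealt with it for efficacy, but left it out of the set meant for safety. That patient is defined by a safety concern after laser, and laser is the only treatment that differs between the arms. The loss is therefore one-sided and related to the outcome being described: it can occur only in Arm 2, and only because something happened after laser.

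The safety of the combination is a secondary objective (Section 2.2), and Section 1.1 presents the laser method as new. An exposure table that omits a patient who received the laser, and an IOP table that omits that patient's post-laser reading, are incomplete for the kind of patient they should describe.

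**Working it through.** **1. Can the case occur?** Section 5.5.4 says that when both treatments are given on one day, "the laser treatment has to be applied at least 30 minutes before the ranibizumab injection". Laser can therefore be given, a concern can arise, and the injection can be withheld. Only Arm 2 receives study laser.

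**2. How is the patient classified?**

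| Set (Section 9.1) | Condition | Laser-only patient |
|---|---|---|
| FAS | Randomized and one injection, or the laser exception | In |
| Safety Set | One injection and one post-baseline safety assessment | Out |

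**3. Are there data to summarise?** Yes. Table 6-1, note i, requires: "On visits when ranibizumab and/or laser treatment is administered, also post-injection tonometry should be performed between 15 and 60 minutes after treatment". The same note requires study-eye tonometry at every visit. Under Section 5.6.2, a patient who stops study treatment without starting a prohibited one stays in follow-up to the end-of-study visit.

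**4. Size per patient.** The planned arm is 28 (Section 9.8).
- Share of the arm: 1/28 = 3.6%. The Safety Set denominator falls from 28 to 27.
- Scheduled post-baseline study-eye IOP readings: 1 after laser on Day 1 + 12 at Months 1 to 12 = 13. This assumes no later laser and follow-up to Month 12.
- If, and only if, the AE tables also use the Safety Set, the event would read 0/27 instead of 1/28. Section 9.5.2.1 names no set for these tables.

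The 28 is a planned minimum. Amendment 2 reports 59 patients already randomized, so the arm may be near 30 and the share near 1/30 = 3.3%.

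**5. How likely is at least one such patient?** The protocol gives no rate, so the rates p below are assumptions. P(at least one among 28) = 1 − (1 − p)^28.

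| Assumed p | P(at least one) |
|---|---|
| 0.1% | 2.8% |
| 0.5% | 13% |
| 1% | 25% |
| 2% | 43% |

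**6. What is not affected?** The patient stays in the FAS, so the primary analysis and the sample size do not change. The by-patient AE listings, and the separate listings of SAEs and of AEs leading to discontinuation, would show the event.

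**The case against.** The strongest reply is that the two sets serve different purposes. The FAS exception rests on the intention to give ranibizumab, which is an intent-to-treat argument. The Safety Set is as treated, and the stated objective concerns ranibizumab alone or combined with laser. A patient who had laser only received neither regimen. This explains how the wording may have arisen, but it does not justify the result. An as-treated set should hold those who received study treatment, and the protocol says that laser is study treatment.

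A second reply is that the case is remote. It needs Day 1 laser before the injection, a concern in that gap, and no injection through Month 11. Laser may be postponed or staged, and entry requires a CSFT above 300 µm, while 300 µm or more is itself a re-treatment criterion. This stands. It is why the point is minor and why the table of assumed rates includes a low value.

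Third, the 13 readings are a maximum. A patient who starts a treatment that requires study withdrawal might have only the post-laser and end-of-study readings. This also stands.

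Fourth, dosing in Section 9.5.2.4 might mean injection only, since Section 6.5.1 ties post-treatment IOP to ranibizumab. But Section 6.3 speaks of dosing for both ranibizumab and laser. Even on the narrow reading, the by-visit ocular summaries and the exposure tables still omit the patient.

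Finally, the definition cannot be treated as a detail left to the SAP. Section 9.1 defers the protocol deviations to the SAP but states the Safety Set in full.

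**Conclusion.** The definition is wrong as written, and the point is minor. A patient whom the protocol itself foresees, who received study treatment and had a safety concern after it, is excluded from the exposure, procedure and ocular/IOP summaries, in Arm 2 only. With no such patient there is no effect, and the tables concerned are descriptive.

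Exclusion from the AE tables cannot be asserted, because the text does not say which set they use. The exclusion itself follows from the wording. Only its likelihood rests on assumed rates.

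**What to change.** In Section 9.1, define the Safety Set as all patients who received at least one study treatment, ranibizumab or laser, and had at least one post-baseline safety assessment. State that a patient who received study laser is summarised under the combination arm. This fits the existing as-treated rule, because that arm is the only one with study laser. In Section 9.5.2.1, name the Safety Set for the AE tables. A footnote can mark any patient who had laser only, so that the table does not suggest an injection was given.

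Leave the FAS definition and the primary count as they are. The cost is one definition and one cross-reference, with no new data, visits or patients.
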